## 2 PROTOCOL SYNOPSIS

Title	Phase I/II clinical trial of Daratumumab in patients with relapsed acute myeloid leukemia post-allogeneic hematopoietic stem cell transplant.
Protocol Short Title	Daratumumab in post-transplant relapse
Name of Drug	Daratumumab
Study Rationale	

1. IFN-<math>\gamma</math> promotes graft-versus-leukemia effects without directly interacting with leukemia cells in mice after allogeneic hematopoietic cell transplantation.

2. Endogenous IFN-gamma levels are elevated in post-transplant patients post-conditioning, infections, GVHD, and during hematopoietic regeneration.

3. We hypothesize that (i) IFN-gamma levels will be higher in post-transplant patients than healthy donors (ii) combination of Daratumumab and endogenous IFN-gamma will mediate antileukemic efficacy post-transplant (iii) the combination of Dara and donor lymphocytes will provide potent effectors, recruit effectors to marrow and mediate GVL.

Treatment Duration	8 weeks; Daratumumab may be continued beyond 8 weeks if clinical benefit is observed up to 12 months.
Dosing Schedule	Weekly Dara for 8 doses
Route	Intravenous
Age range	$\geq 18$ years
Study Duration	10 months to 3.5 years for phase I; 24 months for phase II.
Sample size	8-40 patients for Phase I; 25 patients for phase II
Inclusion Criteria	

1. Patients <math>\geq 18</math> years

2. AML relapse following Allo-HSCT (Morphological relapse, or MRD positive verified by flow cytometry, cytogenetics, and molecular mutations)

Date of protocol: 10/14/2020

IRB Approval Date: 11/24/2020

Version of protocol: 7

IND number: 139015

Institutional protocol number: OSU 17102

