Date of protocol: 10/14/2020

IRB Approval Date: 11/24/2020

Version of protocol: 7

IND number: 139015

Institutional protocol number: OSU 17102

DLT definition	

• Acute GVHD <math>\geq</math> Grade 3

• Any non-hematologic toxicity <math>\geq</math> Grade 3 related to Daratumumab

• Hematologic toxicity: grade 4 toxicity not related to the underlying disease and not responding to growth factor or transfusion within 7 days

• Grade 3 or higher non-neurologic immune-related adverse events (e.g. diarrhea, pruritus, rash) that responds to corticosteroids and improve to grade 1 or less within 4 weeks will NOT count as DLTs. Optional biopsy of affected organs will be encouraged to help determine whether the immune-related condition is due to GVHD

Enrollment schedule	
Dose level 1: Weekly Dara for eight doses; if no infusional toxicity observed or GVHD observed, proceed to next dose level. 3 patients at a time can be enrolled in one dose level.
 
If no GVHD is observed after at least 2 weeks after DLI, enrollment will proceed to next dose level.

Definitions for safety-evaluability	Received at least one dose of Daratumumab
Definition for DLT evaluability	
All patients are evaluable for DLT except patients who are unable to receive 3 doses of daratumumab in dose level 1, or 3 doses of daratumumab and DLT for dose levels 2 and 3 due to progression of AML.
 
DLT observation period will be from the first dose of daratumumab till 7 days post 3rd dose of daratumumab (for dose level 1) and from the first dose of daratumumab till at least 4 weeks post DLI (for dose level 2 and 3)

Definitions for efficacy evaluability:	All eligible patients who receive at least one dose of Daratumumab, do not withdraw consent, and are evaluated for response at week 8.
Dose-limiting toxicity:	Grade 3 or 4 GVHD
Special situations	

1. If patients attain response before DLI, there will be three options at the discretion of treating physician :

a. Proceed with DLI

Date of protocol: 10/14/2020

IRB Approval Date: 11/24/2020

Version of protocol: 7

IND number: 139015

Institutional protocol number: OSU 17102

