## 7 STUDY DESIGN

### 7.1 OVERVIEW OF STUDY DESIGN

This is a phase I/II study that evaluates combination of Daratumumab and escalating doses of donor lymphocyte infusions. Donor lymphocyte infusions will be given within 72 hrs. of daratumumab dose. The following dose levels are used.

1. Phase I study with the following dose levels for related sibling donors:
  - a. Dose level 1: Dara 16mg/kg
  - b. Dose level 2: Dara 16mg/kg + DLI (1 infusion at any time between weeks 3-5) : 1x10e6 CD3/kg
  - c. Dose level 3: Dara 16mg/kg + DLI (1 infusion at any time between weeks 3-5): 1x10e7 CD3/kg
2. Phase I study with the following dose levels for unrelated donors:
  - c. Dose level 1: Dara 16mg/kg
  - d. Dose level 2: Dara 16mg/kg + DLI (1 infusion at any time between weeks 3-5): 1x10e5 CD3/kg
  - e. Dose level 3: Dara 16mg/kg + DLI (1 infusion at any time between weeks 3-5): 1x10e6 CD3/kg
3. Phase I study with the following dose levels for haploidentical donors:
  - f. Dose level 1: Dara 16mg/kg
  - g. Dose level 2: Dara 16mg/kg + DLI (1 infusion at any time between weeks 3-5): 1x10e4 CD3/kg
  - h. Dose level 3: Dara 16mg/kg + DLI (1 infusion at any time between weeks 3-5): 1x10e5 CD3/kg

Patients with MRD will not be enrolled until the DLT period for dose level 1 has been completed and it has been determined that the treatment schedule is safe. Patients must be positive for MRD disease as

Date of protocol: 10/14/2020

IRB Approval Date: 11/24/2020

Version of protocol: 7

IND number: 139015

Institutional protocol number: OSU 17102

[figure not shown]
determined by the combined analyses of flow cytometry, genomic sequencing and cytogenetics. Patients who do not demonstrate evidence of MRD in all three methods will not be eligible for the trial.

Bone marrow biopsies are done at the completion of 8 weeks. The maximal tolerated dose of DLI is chosen for expansion to the phase II portion of the study.

If patients are found to be in CR at the end of 8 weeks and treating physician concludes that patient continues to benefit from treatment, patients may proceed to Daratumumab maintenance with a schedule of 16mg/kg every 2 weeks for 16 weeks (8 doses) and then monthly for 6 months .

For patients with rapidly progressive disease despite 4 doses of Daratumumab, they will come off trial.

The dose level that is deemed safe will be chosen for the phase II portion of the study.

Dose level	Sibling donor	Unrelated donor	Haploidentical donor

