## 8 STUDY POPULATION

### 8.1 INCLUSION CRITERIA

1. Age  $\geq$  18 years
2. AML or MDS relapse following Allo-HSCT (Morphological relapse, or MRD positive by flow cytometry, cytogenetics, and molecular mutations)
3. Patients who received a 10/10 HLA-matched allogeneic HCT either from sibling donors or unrelated donors or at least a 5/10 haploidentical transplant for Dose level 2 and 3
4. Patients with R/R AML must not be candidates for available therapies known to be effective for treatment of their AML.
5. For patients in Dose level 1 (Daratumumab only), relapsed refractory AML patients who have previously not received an allogeneic HCT are eligible.
6. Engraftment must have occurred as defined by platelet (PLT) count  $> 20,000/\mu\text{L}$  and ANC  $\geq 0.5$
7. ECOG performance status  $< 3$
8. Creatinine clearance  $> 40 \text{ ml/min}$  (Calculated or measured)
9. Aspartate aminotransferase (AST)  $< 3 \times$  upper limit of normal (ULN), alanine aminotransferase (ALT)  $< 3 \times$  ULN, and total bilirubin  $< 1.5 \times$  ULN
10. Off calcineurin inhibitors for at least 2 weeks
11. Prednisone dose  $\leq 20 \text{ mg/day}$ .
12. Patients with proliferative disease can be cytoreduced with cytotoxic chemotherapy at investigator's discretion, but there should be at least a 14 day window between start of cytoreductive therapy and start of Daratumumab
13. Blast count  $< 20 \text{ K/day}$  (hydrea use is allowed)
14. Patient willing to agree to study-related research marrows
15. Female patients of childbearing potential who are sexually active must be willing to use an effective barrier method of birth control to avoid pregnancy during the study and for a minimum of 3 months after stopping study treatment
16. Male patients with partners of childbearing potential who are sexually active must be willing to use an effective barrier method of birth control to avoid pregnancy during the study and for a minimum of 3 months after stopping study treatment

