### 8.2 EXCLUSION CRITERIA

1. No demonstrable evidence of donor chimerism ( $< 55$  donor CD3 or CD33 chimerism)
2. Patients with a molecular mutation without chromosomal abnormalities or declining chimerisms (MRD status must be verified by surface marker and mutational analyses)
3. Active graft-versus-host disease (GVHD) grades I-IV; prior acute GVHD could have occurred but resolved at time of initiation of Daratumumab
4. Extensive chronic GVHD requiring ongoing immunosuppression with calcineurin inhibitors or more than 20 mg of prednisone
5. Patients with FLT3+ AML or blast crisis CML who have not yet received post-transplant TKI therapy

6. Active CNS or testicular disease
7. Subject is:
  - 7.2 seropositive for human immunodeficiency virus (HIV)
  - 7.3 seropositive for hepatitis B (defined by a positive test for hepatitis B surface antigen [HBsAg]).  
Subjects with resolved infection (ie, subjects who are HBsAg negative but positive for antibodies to hepatitis B core antigen [anti-HBc] and/or antibodies to hepatitis B surface antigen [anti-HBs]) must be screened using real-time polymerase chain reaction (PCR) measurement of hepatitis B virus (HBV) DNA levels. Those who are PCR positive will be excluded. EXCEPTION: Subjects with serologic findings suggestive of HBV vaccination (anti-HBs positivity as the only serologic marker) AND a known history of prior HBV vaccination, do not need to be tested for HBV DNA by PCR.
8. seropositive for hepatitis C (except in the setting of a sustained virologic response [SVR], defined as aviremia at least 12 weeks after completion of antiviral therapy).
9. Patients must not have chronic obstructive pulmonary disease with a forced expiratory volume in 1 second (FEV1) < 50% of predicted normal. FEV1 is required for patients suspected of having chronic obstructive pulmonary disease and are not eligible if FEV1 is < 50% of predicted normal.
10. Patients must not have moderate or severe persistent asthma within the past 2 years and must not have currently uncontrolled asthma of any classification.
11. Active autoimmune disease prior to transplant
12. Female patients of childbearing potential who are sexually active and unwilling to use an effective barrier method of birth control to avoid pregnancy during the study and for a minimum of 3 months after study treatment.

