### 16.2 Analysis methods:

Analysis datasets:

Efficacy sets: All evaluable patients will be included in the analysis of the primary endpoint. The term evaluable is defined as any eligible patient who receives at least one dose of Daratumumab, does not withdraw consent, and is evaluated for response week 8; patients who fail to have a week-8 assessment due to early progression, death or toxicity will also be considered evaluable for response and categorized as non-responders. Patients who fail to have a week-8 assessment for other reasons (e.g., refusal due to travel constraints) will be considered unevaluable and will not be included in the denominator when calculating ORR rate.

Safety sets: The safety analysis dataset will include all eligible patients who receive one dose of daratumumab.

The adverse events will be examined and worst grade adverse events will be recorded for each patient and summarized by type, severity, and attribution (if possible) using NCI CTCAE version 4 criteria. Tolerability of the regimen will be assessed by summarizing the number of patients who require dose modifications and/or dose delays. In addition, we will also capture the proportion of patients who go off treatment due to adverse events or even those who refuse further treatment for lesser toxicities that inhibit their willingness to continue participation on the trial. All patients who have received at least one dose of daratumumab will be evaluable for toxicity and tolerability.

The primary endpoint of phase II is to evaluate overall response rates (ORR) to the combination of Daratumumab and DLI. The ORR will be defined as complete remission (CR), complete remission with incomplete marrow recovery (CRi), partial remission (PR) and morphological leukemia free

Date of protocol: 10/14/2020

IRB Approval Date: 11/24/2020

Version of protocol: 7

IND number: 139015

Institutional protocol number: OSU 17102

state (MLFS). The proportion of patients achieving ORR among efficacy sets will be calculated and 95% confidence interval will be estimated. In addition, the ORR among patients who received at least 3 doses of Daratumumab and DLI will be calculated as well. The ORR rate among MRD positive patients and patients with overt morphological relapse will be estimated as well. The MRD conversion rate from MRD positive to MRD negative, and the 3-month GVHD rate (both grade II-IV and III-IV) will be similarly analyzed.

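### The pooled primary ORR has no rule for patients who enter MRD-positive without morphologic relapse; read literally, an unchanged patient counts towards the 6 responders

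*Combined protocol and SAP*

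**What the plan says.** **Entry.** Synopsis inclusion criterion 2 admits "AML relapse following Allo-HSCT (Morphological relapse, or MRD positive verified by flow cytometry, cytogenetics, and molecular mutations"), and section 8.1 item 2 admits "AML or MDS relapse following Allo-HSCT (Morphological relapse, or MRD positive by flow cytometry, cytogenetics, and molecular mutations"). MRD positivity is therefore a qualifying form of relapse on its own. Section 7.1 limits when and how such patients enter: "Patients with MRD will not be enrolled until the DLT period for dose level 1 has been completed", and "Patients who do not demonstrate evidence of MRD in all three methods will not be eligible for the trial". Section 8.2 item 2 excludes "Patients with a molecular mutation without chromosomal abnormalities or declining chimerisms (MRD status must be verified by surface marker and mutational analyses"). No cap or expected share of MRD-only patients is given.

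**Primary endpoint.** Section 16.2 states: "The ORR will be defined as complete remission (CR), complete remission with incomplete marrow recovery (CRi), partial remission (PR) and morphological leukemia free" state. The analysis is pooled: "The proportion of patients achieving ORR among efficacy sets will be calculated and 95% confidence interval will be estimated". Section 16 rejects a 10% response rate if 6 or more of 25 patients respond.

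**Secondary endpoints.** Sections 6.2 and 16.1 list ORR in MRD-positive patients, ORR in overt morphologic relapse and, separately, the MRD conversion rate. ORR in MRD-positive patients has no definition of its own.

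**Response criteria.** The efficacy row of the synopsis refers only to the usual AML response assessment and names no source. The response form in the appendix sends its user back to the protocol for definitions, and the protocol contains none. The on-treatment form offers CRc, CRm, SD and Relapse alongside CR, CRi, PR and MLFS, without saying which of them count as response.

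**The concern.** The four categories in the ORR describe marrow morphology. A patient in morphologic relapse has to improve to reach any of them. A patient who enters with MRD only has no morphologic disease at baseline and may meet one of them on day 1. If nothing changes by week 8, the literal definition counts that patient as a responder.

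The 6-responder rule is the only test of the primary endpoint, and each such patient moves the count by one. Suppose three MRD-only patients are unchanged. If the other 22 yield 3, 4 or 5 responders, the total is 6, 7 or 8 on the literal reading (reject) and 3, 4 or 5 if those three are non-responders (do not reject). The planned subgroup ORRs would show the case mix but not which count decides the trial. Section 16.3 has the study team discussing accumulating efficacy data monthly in phase II, so a rule settled later could be chosen with responses in view.

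**Working it through.** **Step 1. The plan's own figure.** Inputs from section 16: n = 25, cutoff 6, null rate 10%, alternative 30%, alpha 0.05, power 0.80. With X ~ Binomial(25, p):

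- P(X ≥ 6 | p = 0.10) = 0.0334
- P(X ≥ 6 | p = 0.30) = 0.8065

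Both meet the stated targets, and 25 is the smallest n that meets them exactly (one-sided). The design arithmetic is sound. The question is what gets counted.

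**Step 2. The literal reading.** Two inputs are assumed because the documents give neither:

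- m: number of MRD-only patients among the 25
- q: probability that such a patient is still in morphologic remission at week 8 without drug effect, taken as 0.2 to 0.7

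The other 25 − m patients respond at the 10% null rate. Then

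P(positive) = Σₓ P(Bin(m, q) = x) × P(Bin(25 − m, 0.10) ≥ 6 − x), x = 0, …, m.

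For m = 3, the chance of at least 6, 5, 4 or 3 responders among the other 22 is 0.0182, 0.0621, 0.1719 and 0.3800. At q = 0.7 the weights for x = 0, 1, 2, 3 are 0.027, 0.189, 0.441 and 0.343, so

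0.027×0.0182 + 0.189×0.0621 + 0.441×0.1719 + 0.343×0.3800 = 0.218.

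| m | q = 0.2 | q = 0.5 | q = 0.7 | q above which P exceeds 0.05 |
|---|---|---|---|---|
| 1 | 0.039 | 0.056 | 0.068 | about 0.39 |
| 2 | 0.046 | 0.090 | 0.127 | about 0.23 |
| 3 | 0.053 | 0.138 | 0.218 | about 0.19 |
| 5 | 0.069 | 0.272 | 0.485 | about 0.15 |

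**Step 3. The reference value.** Under a rule that requires improvement, the null hypothesis gives MRD-only patients the same 10% rate as everyone else. Setting q = 0.10 returns 0.0334 for every m, so 0.033 is the comparator.

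**Step 4. How often the readings disagree.** With three unchanged MRD-only patients and 10% response in the other 22, P(3, 4 or 5 responders) = 0.208 + 0.110 + 0.044 = 0.36.

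**Step 5. Analysed sample size.** Sections 16 and 7.2 enrol 25, section 16 allows for 10% unevaluable, and it adds 3 to 6 phase I patients treated at the MTD. That gives 22.5 + 3 to 22.5 + 6, or roughly 25 to 28 analysed. With cutoff 6 and no MRD-only patients, P(6 or more) at 10% is 0.033 at n = 25 and 0.055 at n = 28. The table therefore applies to n = 25 and would shift with the final number.

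**The case against.** The best argument against the concern is that the protocol's language favours non-response. The phase II objective is response to treatment. MRD positivity is listed as relapse. The synopsis provides for the case "If patients attain response before DLI, there will be three options", and that verb means little if an MRD-only patient is in response from the start. Section 16.2 also speaks of patients achieving ORR. This stands as evidence of intent, and a reader should not infer that the sponsor plans to count unchanged patients. It does not amount to a rule: section 16.2, the only place that defines ORR, omits any condition on entry status, and neither the synopsis nor the forms supply one.

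A second argument is that the numbers may be small. Section 7.1 requires MRD by all three methods, section 8.2 excludes some molecular-only cases, and section 16.2 already treats a week-8 assessment missed through early progression, death or toxicity as non-response. This also stands. At q = 0.2, one or two MRD-only patients leave the probability below 0.05. Even so, two secondary endpoints concern MRD-positive patients, so the plan expects some.

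Third, a reader might infer that alpha was miscalculated or that the type I error is inflated. The documents do not support that. If the literal definition is accepted, m = 5 and q = 0.7 give a true pooled rate of (5×0.7 + 20×0.1)/25 = 22%, and rejecting 10% is then correct for that endpoint. The fault is that the result could not be attributed to treatment.

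Finally, it is tempting to widen the contrast by assuming that MRD-only patients contribute no responders under the stricter reading (0.011 at m = 5). That reading denies response only to unchanged patients, so 0.033 is the fair comparator.

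**Conclusion.** The point holds as a gap in the primary endpoint definition that can change the primary decision. Applied literally, section 16.2 credits an MRD-only patient who is unchanged at week 8. Other wording points the other way, and nothing settles it.

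The chance of a positive trial without drug effect is 0.046 to 0.127 with two such patients, 0.053 to 0.218 with three and 0.069 to 0.485 with five, against 0.033. These figures assume 25 analysed patients, 10% response in the others and q between 0.2 and 0.7. Neither m nor q can be taken from the documents, so the ranges show sensitivity and do not predict what will happen. A near-certain false success would need about six or more unchanged MRD-only patients, and nothing in the plan shows that this is likely. The stated sample size and cutoff are correct for 10% against 30%. This should be fixed before phase II responses are known; confidence in its practical size is medium.

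**What to change.** Add to section 16.2, for the primary ORR only:

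- A patient who is MRD-positive without morphologic relapse at entry, and who remains MRD-positive in morphologic remission at week 8, is a non-responder.
- Such a patient counts as a responder only on conversion to MRD-negative on the week-8 marrow, by a named assay or assays. Section 7.1 uses three methods for entry and section 8.2 names two kinds of analysis, so the choice must be stated.
- Patients in morphologic relapse at entry keep CR, CRi, PR or MLFS.
- Each form code, including CRc, CRm, SD and Relapse, is mapped to responder or non-responder.
- In the MRD-only stratum, ORR and the MRD conversion rate are then the same quantity.

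The cost is a short amendment. Section 10.1 already plans the week-8 marrow and the conversion endpoint already needs an MRD result, although the study calendar lists no MRD assay.

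There are statistical costs:

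- ORR will be lower than under the literal reading and becomes a composite.
- With 30% response in the others, power falls below 0.80 if conversion on treatment is under 30%. At 20% conversion it is 0.78 (m = 2), 0.77 (m = 3) and 0.74 (m = 5); at 10% it is 0.76, 0.73 and 0.67.
- The chance of a positive trial without drug effect exceeds 0.05 if background conversion is above about 0.23 (m = 2), 0.19 (m = 3) or 0.15 (m = 5).

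An alternative is to limit the test to patients in morphologic relapse and report MRD-only patients separately. It avoids the composite, but the sample size and cutoff would have to be re-derived for that group, so it is the more expensive change.

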1. CBC, CMP

End-of-study visit

1. CD3 CD33 peripheral blood chimerisms

Long-term follow-up to 6 months will occur – at month 3 and at month 6. These visits will be done when patient is evaluated by their treating physician.

Date of protocol: 10/14/2020

IRB Approval Date: 11/24/2020

Version of protocol: 7

IND number: 139015

Institutional protocol number: OSU 17102

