## **12.2 DISEASE ASSESSMENT TIMELINES**

Disease assessment will be performed at the following time points:

Screening for trial

Bone marrow biopsy pre-DLI

End of study bone marrow biopsy

In addition, bone marrow biopsies can be performed at the discretion of the primary physician.

Date of protocol: 10/14/2020  
Version of protocol: 7  
IND number: 139015  
Institutional protocol number: OSU 17102

IRB Approval Date: 11/24/2020

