Demographical and clinical characteristics of study patients will be described using mean and standard deviation, median and range, or frequency and percent depending on the data type and distribution. Overall survival (OS) will be defined as the time from the first treatment of Daratumumab to death or last contact date if no death. Progression free survival (PFS) will be defined as the time from the first treatment of Daratumumab to the date of progression or death or last clinical assessment date if no progression or death. Kaplan-Meier curves will be generated to estimate OS/PFS at 6 months. The association between patient characteristics and OS/PFS will be evaluated in univariable Cox proportional hazard regression model.

To examine the rate of GVHD (both grade II-IV and III-IV), the event will be onset of GVHD and time to GVHD will be defined as the period of time from first treatment of Daratumumab to the onset of GVHD. Death and early relapse without GVHD will be competing risks. Cumulative incidence rate of GVHD at 3-month with 95% confidence intervals will be estimated from the cumulative incidence curves. Competing risk regression analysis will be conducted to estimate the association between patient characteristics and GVHD.

For pre/post-treatment comparisons in the correlative part of the study, a paired t-test will be applied. Two-tailed p values <0.05 will be considered statistically significant in all analyses.

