## GVHD assessment at baseline

	Acute GVHD	Chronic GVHD
Current state	Currently active - Yes or No	Currently active - Yes or No
Grade	Current grade	Current grade
Grade	Maximal grade	Maximal grade
Prednisone	Yes or No, dose if yes	Yes or No, dose if yes
Other immunosuppression	Yes or No	Yes or No

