## 17102\_AML On Treatment

## 17102\_AML\_On\_Treatment

Date of Hospital Admission	
Date of Hospital Discharge	
Number of days of GCSF	
Received ESA?	Option List Name: YES_NO; Option List Items: *, No, Not Applicable, Unknown, Yes
Number of PRBC units	
Number of platelet units	
Demonstrated refractoriness to platelet transfusion?	Option List Name: YES_NO; Option List Items: *, No, Not Applicable, Unknown, Yes
Does the patient currently have an infection?	Option List Name: YES/NO; Option List Items: No, Yes
If current Infection Yes, please specify	Option List Name: 14040; Option List Items: Bacterial, Controlled, Fungal, Uncontrolled, Viral
If current Infection Yes, please specify type	Option List Name: 14040; Option List Items: Bacterial, Controlled, Fungal, Uncontrolled, Viral
Response	Option List Name: AML_RESPONSE_CRITERIA; Option List Items: Complete remission (CR), CR with incomplete recovery (CRi), Cytogenetic CR (CRc), Death from indeterminate cause, Death in aplasia, Molecular CR (CRm), Morphologic leukemia-free state, Not assessed, Partial remission (PR), Relapse, Resistant disease (RD), Stable Disease (SD)
Treatment Failure?	Option List Name: YES/NO; Option List Items: No, Yes
If Treatment Failure Yes, please specify	Option List Name: AML_RESPONSE_CRITERIA; Option List Items: Complete remission (CR), CR with incomplete recovery (CRi), Cytogenetic CR (CRc), Death from indeterminate cause, Death in aplasia, Molecular CR (CRm), Morphologic leukemia-free state, Not assessed, Partial remission (PR), Relapse, Resistant disease (RD), Stable Disease (SD)
Was treatment plan interrupted?	Option List Name: YES/NO; Option List Items: No, Yes
If treatment plan interrupted Yes, please explain	
Was dose modified?	Option List Name: YES/NO; Option List Items: No, Yes
If dose modified Yes, please explain	
Other details	

Date of protocol: 10/14/2020  
Version of protocol: 7  
IND number: 139015  
Institutional protocol number: OSU 17102

IRB Approval Date: 11/24/2020

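### Off maintenance, no disease test is required after the week-8 marrow, yet 6-month PFS is censored at the last clinical assessment, which tends to overstate it

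*Combined protocol and SAP*

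**What the plan says.** Sections 6.2 and 16.1 list 6-month PFS as a secondary endpoint of phase II. Section 16.2 says "Kaplan-Meier curves will be generated to estimate OS/PFS at 6 months" and measures PFS from the first daratumumab treatment "to the date of progression or death or last clinical assessment date if no progression or death".

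The passages that say when disease is looked for are these:

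- **Section 12.2** names three time points: screening, a marrow before DLI, and the "End of study bone marrow biopsy". Any further marrow is left to the physician.
- **Sections 7.1 and 10.1** place the last of these marrows at week 8. The calendar in 12.1.3 puts it in the Day 57-71 column, where, as far as the table can be read, only the clinical and research marrows are ticked.
- **Section 12.1.2** plans long-term follow-up at month 3 and month 6 and says only that "These visits will be done when patient is evaluated by their treating physician". It lists no test for either visit.
- **Section 12.1.3, maintenance calendar,** schedules a CBC at every visit from Week 9 to Week 45. Marrows during maintenance are discretionary.
- **Section 12.5** keeps patients in remission under clinic follow-up for GVHD and safety, and follows all patients for survival. It does not require a disease assessment.

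**The concern.** A Kaplan-Meier estimate of PFS is only as good as the observation of progression behind it. If a patient counts as progression-free up to a visit at which nobody was required to look for leukemia, the patient stays in the risk set without an event whether or not the disease has returned. Progression that is found late is dated late, and progression never looked for before the 6-month landmark is missed at that landmark. Both errors push the estimate the same way, towards a higher 6-month PFS. In a single-arm trial there is no control group in which the same error could offset it.

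**Working it through.** **Plan's own figure.** The documents give no expected 6-month PFS and no precision for it, so there is nothing to reproduce. The phase II sample size is built on response and is not in question here.

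**1. Where the landmark falls.** PFS starts at the first dose (Day 1, section 16.2). Six months is 365.25 / 2 = 182.6 days, so the landmark is at 1 + 182.6 = about Day 183.6.

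**2. Which marrow is the last required one.** Section 12.4 lets study completion mean the end of a 6-month follow-up, so the end-of-study marrow of 12.2 could be read as a late one. Three places point to week 8 instead: section 10.1 lists consent, pre-DLI and week 8; section 7.1 puts the biopsy at the completion of 8 weeks; and section 12.1.2 lists the end-of-study visit separately from long-term follow-up. Week 8 is the natural reading, but the plan should say so.

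**3. Interval without a required disease test, off maintenance.**

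- From Day 71: 183.6 - 71 = about 113 days.
- From Day 57: 183.6 - 57 = about 127 days.

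**4. What the censoring rule does with that interval.** Take a patient off maintenance with no progression at the week-8 marrow, seen at month 3 and month 6 with no test for leukemia.

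| Censoring rule | Progression-free time credited to |
|---|---|
| Last clinical assessment (16.2 as written) | Month-6 visit |
| Last disease assessment | Day 57-71 |

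If the month-6 visit falls at the landmark, the first rule credits about 113 to 127 days that no required test supports.

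**5. Direction and unit of error.** As an illustration, assume 25 patients are analysed and none is censored before the landmark. Each progression that occurs before the landmark but is not recorded by then raises the 6-month estimate by 1 / 25 = 4 percentage points. The documents give no basis for the number of such patients.

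**6. Who is affected.** On maintenance, Week 9 begins on Day 1 + 8 × 7 = 57 and Week 25 on Day 1 + 24 × 7 = 169. The calendar has CBCs at Weeks 9, 11, 13, 15, 17, 19, 21, 23 and 25, which is nine before the landmark. Section 7.1 opens maintenance after week 8 to patients in CR whom the physician judges to benefit. The gap therefore concerns patients alive and without progression at week 8 who are not on maintenance.

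**The case against.** The strongest reply is that few progressions will be missed. Section 4.1 cites median post-relapse survival of 51 days with chemotherapy and 84 days with DLI, so many PFS events should come early. Rapid progressors leave the trial after 4 doses (sections 7.1 and 16.3), the week-8 marrow catches others, and deaths count as events through survival follow-up. Patients on maintenance have regular blood counts, and the hematology form has a field for blasts. A treating physician would probably order a blood count at months 3 and 6 anyway.

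Most of this stands, and it limits the size. It does not remove the problem: nothing requires those counts off maintenance, and the censoring rule does not ask whether they were done.

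A reader might infer more from the same passages. The documents do not support these stronger readings:

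- *That most of the 6-month window is unobserved for everyone.* The interval in the working applies off maintenance only. It is a stretch of calendar time, not a share of events.
- *That PFS, MRD conversion or GVHD cannot be obtained from the forms.* Relapse and resistant disease are response options, and the response form has an assessment date. The adverse event form takes GVHD onset and grade, even though the only dedicated GVHD form is "GVHD assessment at baseline". Cytogenetic CR, molecular CR and karyotype give partial information on MRD. A dated progression option, an MRD result and a Glucksberg grade are missing details.
- *That cytogenetic and molecular CR are non-responses.* Both are labelled as kinds of CR, ORR counts CR, and nothing excludes them. The mapping is simply not written down.
- *That a post-transplant relapse date is needed.* Section 16.2 starts OS and PFS at the first daratumumab treatment.

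**Conclusion.** The point holds for patients not on maintenance. After the week-8 marrow the plan requires no disease assessment from them, and its censoring rule credits progression-free time at visits with no stated content. For them, about 113 to 127 days before the 6-month landmark carry no required test. The likely effect is an upward bias in 6-month PFS. Its size cannot be estimated, because the documents do not say how many patients will be off maintenance and progression-free at week 8, or what testing they will receive in practice.

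This rests on reading the end-of-study marrow as the week-8 marrow, and on the calendar ticks as they appear in the extracted table. It affects a secondary endpoint that is estimated, not tested against a threshold. It is worth correcting because the correction is cheap and is best made before data accrue.

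**What to change.** Make two changes together:

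1. **Section 12.1.2:** require a CBC with blast differential at the existing month-3 and month-6 visits for all patients still in follow-up without progression. State the date from which these months are counted. Six months after the Day 50 dose would be about Day 50 + 182.6 = 233, later than the PFS landmark.
2. **Section 16.2:** censor PFS at the last disease assessment (CBC with differential or marrow) instead of the last clinical assessment.

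The second change alone would censor patients off maintenance at Day 57-71 unless discretionary tests were done, leaving few at risk at 6 months. The first alone would leave untested visits counting as progression-free.

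The cost is a blood count at two existing visits, slightly earlier censoring for some patients, and a few lines of text. No extra marrow is needed. A blood count is a minimum: it can miss marrow-only or MRD-level disease, so the bias is reduced, not removed.

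As housekeeping only: state that the end-of-study marrow in 12.2 is the week-8 marrow; add a dated progression option, an MRD result field and a Glucksberg GVHD grade field; and state that CRc and CRm count as CR for ORR.
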